8.2.7. Subjects with complete remission of tics on the YGTSS-TTS

Subjects with complete remission of tics on the YGTSS-TTS (i.e. YGTSS-TTS=0) at any time between the Baseline visit and the Week 12 visit will be considered as Responders. Any subject who has at least 1 Response will be considered as a Responder; otherwise the subject will be considered a Non-Responder.

Statistical analysis:

The percentage of subjects with complete remission of tics on the YGTSS-TTS will be analyzed through a logistic regression model to obtain an estimate of the population odds ratio and associated confidence intervals between ecopipam and matching placebo. The model will include fixed effects for treatment, center, and covariate for baseline YGTSS-TTS score.

Summary statistics will be presented along with a full data listing.

8.2.8. Change in YGTSS-TTS from Baseline to Weeks 4, 6, and 8

A secondary analysis will be performed on the change in YGTSS-TTS from Baseline to Weeks 4, 6 and 8.

Statistical analysis:

The analysis method will be the same as the primary efficacy analysis as described in **Section 8.1.1.**, with the treatment difference at weeks 4, 6, and 8 estimated based on MMRM.

Summary statistics will be presented along with a full data listing by treatment group.

8.2.9. Change in CGI-TS-S from Baseline to Weeks 4, 6, and 8

A secondary analysis will be performed on the change in CGI-TS-S from Baseline to Weeks 4, 6 and 8.

Statistical analysis:

The analysis method will be the same as the primary efficacy analysis as described in **Section 8.1.1.**, with the treatment difference at weeks 4, 6, and 8 estimated based on MMRM.

Summary statistics will be presented along with a full data listing by treatment group.

8.2.10. CGI-TS-I at Week 4, 6, and 8

A secondary analysis will be performed on the CGI-TS-I at Weeks 4, 6 and 8.

Statistical analysis:

The analysis method will be the same as the primary efficacy analysis as described in **Section 8.1.1.**, with the exception of no baseline score will be used as a covariate. The treatment difference at weeks 4, 6, and 8 will be estimated based on MMRM.

Summary statistics will be presented along with a full data listing by treatment group.

8.2.11. Change in YGTSS-GS from Baseline to Weeks 4, 6, and 8

A secondary analysis will be performed on the change in YGTSS-GS from Baseline to Weeks 4, 6 and 8.

Statistical analysis:

The analysis method will be the same as the primary efficacy analysis as described in **Section 8.1.1.**, with the treatment difference at weeks 4, 6, and 8 estimated based on MMRM.

Summary statistics will be presented along with a full data listing by treatment group.

8.2.12. Change in CaGI-C from Baseline to Weeks 4, 6 and 8

See section 8.2.4 for a description of the Caregiver Global Impression of Change (CaGI-C).

A secondary analysis will be performed on the CaGI-C at Weeks 4, 6 and 8.

Statistical analysis:

The analysis method will be the same as the primary efficacy analysis as described in **Section 8.1.1**, with the exception of no baseline score will be used as a covariate. The treatment difference at weeks 4, 6, and 8 will be estimated based on MMRM.

Summary statistics will be presented along with a full data listing by treatment group.

8.2.13. Change in the C&A-GTS-QOL from Baseline to Weeks 4, 6, and 8

See section 8.2.5 for a description of the Gilles de la Tourette Syndrome–Quality of Life Scale for Children and Adolescents (C&A-GTS-QOL). A secondary analysis will be performed on the change in C&A-GTS-QOL VAS and total score from Baseline to Weeks 4, 6 and 8.

Statistical analysis:

The analysis method for the VAS and total score will be the same as the primary efficacy analysis as described in **Section 8.1.1.**, with the treatment difference at weeks 4, 6, and 8 estimated based on MMRM.

Summary statistics for the VAS, subscales, and total score will be presented along with a full data listing by treatment group.

8.3 COVID-19 Analyses

Due to COVID-19 pandemic, additional analyses will be conducted:

- The amount of missing data by treatment group and overall by endpoint for data missing due to COVID-19 will be summarized in a table.
- Efficacy endpoint analyses will have additional analysis modeling using the terms *Remote* (Yes/No) and *Type* (Audio/Video), to account for any bias that these data collection methods may have introduced.

9. Analysis of Pharmacokinetics

Blood samples will be collected to measure concentrations of ecopipam and/or its major (active) metabolites at Weeks 4 and 12.

For the Week 4 visit, a morning appointment is suggested. Parents/caregivers will be instructed not to administer the study medication to the subject on the evening prior to the Week 4 visit and to record the time of administration of the last dose of study medication taken. The study drug administration will occur on the day of the Week 4 visit at the site under the supervision of the study investigator. An intravenous catheter will be placed, and the subject will have samples collected at the following time windows: one sample at predose (34 to 44 hours since the last dose), one sample between 0.5 and 1.5 hour after administration of study medication, and one sample between 2 and 4 hours after study drug administration. Any samples should be collected at least 30 min apart.

For the Week 12 visit, parents/caregivers will be asked to record the time of study drug administration on the evening prior to the visit. An appointment is suggested to be made for the morning of the Week 12 visit. A blood sample will be collected at the end of the visit. The time of sample collection will be recorded. Blood samples will be processed as outlined in the protocol and serum/plasma will be frozen, shipped and analyzed for ecopipam and SCH40853.

Plasma concentration-time data will be summarized in the Clinical Study Report (CSR). Population pharmacokinetic analysis will be conducted and summarized separately, using data from this study along with data from adults using the same tablet formulation (if available). The methodology for these pharmacokinetic analyses will be reported in a separate analysis plan.

10. Safety

The population used for safety analyses will be the Safety Set (SS). Safety will be assessed by monitoring and recording all adverse events (AEs) and Serious Adverse Events (SAEs) (all Visits), regular monitoring of hematology, blood chemistry, and urine values (Screening, Baseline, Week 12 and 7-day and 14-day Follow Up visits). HbA1c will also be measured during these visits except on the 14 day Follow Up visit. Regular measurement of vital signs and the performance of a physical examination and an ECG will occur at Screening, Baseline and Weeks 4, 6, 8 and 12 and 7 day and 14 day Follow Up visits. An additional assessment will include the Columbia-Suicide Severity Rating Scale (C-SSRS) (all Visits except 30 day Follow up visit). Additional safety outcomes (Baseline and Weeks 4, 6, 8 and 12) will include the Abnormal Involuntary Movement Scale (AIMS), the Barnes Akathisia Rating Scale (BARS), the Swanson, Nolan and Pelham (SNAP-IV) questionnaire, the Children's Yale-Brown Obsessive Compulsive Scale (CY-BOCS), the Children's Depression Rating Scale-Revised (CDRS-R), and the Pediatric Anxiety Rating Scale (PARS).

All safety data will be summarized in Safety Set according to the actual treatment.

Treatment-emergent adverse events (TEAEs) are defined as adverse events that are newly occurring or worsening after the first dose of study medication. The incidence of TEAEs will be summarized by treatment group, by severity and by relationship to study medication. Serious TEAEs and TEAEs leading to the study termination will be summarized by treatment group. Laboratory data, vital sign, physical examination and ECG will be summarized by treatment and visit.

10.1. Extent of Exposure

Duration of exposure will be summarized using descriptive statistics by treatment group. The duration of exposure will also be categorized (<7, 7-<14, 14-<28, 28-<42, 42-<56, 56-<70, 70-<84, \geq 84), and tabulated by treatment group. Duration of exposure (weeks) will be calculated as (Date of Last Dose – Date of First Dose) +1. If date of last dose is unknown then the date of last clinical visit will be used.

A listing including study drug administration information from the eCRF will be presented.

10.2. Treatment Compliance

Subjects are expected to take 1 tablet of study medication once per day.

Treatment compliance, as a percentage, will be calculated as compliance (%) = (Sum of Study drug taken= Yes) / (number of days in study) x 100. The number of actual doses taken will be recorded on the eCRF.

Subjects will be considered compliant overall for study medication if the compliance is \geq 80%. Descriptive statistics (number of subjects, mean, SD, minimum, median, and maximum) for number of actual tablets taken, number of expected tablets taken, and treatment compliance will be summarized by treatment group.

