During the 8-week treatment phase, the following ecopipam HCl doses or matching placebo will be administered for each of the weight bands:

- Those who weigh $\geq 18 \leq 23$ kg will receive 37.5 mg daily.
- Those who weigh $>23 \le 34$ will receive 50 mg daily.
- Those who weigh $>34 \le 44$ will receive 75 mg daily.
- Those who weigh $>44-\leq 68$ kg will receive 100 mg daily.
- Those who weigh $>68 \le 83$ kg will receive 150 mg daily.
- Those who weigh >83 kg will receive 200 mg daily.

All doses will be administered once daily in the evening.

At the end of the 8-week treatment phase, subjects will titrate off therapy and receive ecopipam HCl doses or matching placebo that will be reduced by 25 mg/day until off of drug; signs of symptoms of withdrawal will be monitored.

Duration of treatment:

Four weeks Screening Phase, Baseline Visit, 4-week Titration Period, 8-week Treatment Period and 2-week Follow-up Period. There will also be a phone call to subjects 30 days after study completion or early termination to assess any adverse events.

Reference therapy, dosage, and mode of administration:

Placebo-controlled, matching placebo tablets given by mouth (PO) in the evening.

Criteria for evaluation:

Efficacy:

Primary Efficacy Endpoint:

The primary efficacy endpoint is the change in the Yale Global Tic Severity Scale – Total Tic Score (YGTSS-TTS, i.e., sum of the motor and phonic tic scores) from baseline (YGTSS-TTS score from Baseline visit) to end of therapy (YGTSS-TTS score from Week 12).

Key Secondary Efficacy Endpoint:

• Change in Clinical Global Impression of Tourette Syndrome Severity (CGI-TS-S) from Baseline to Week 12

Other Secondary efficacy endpoints include:

- Change in Clinician Global Impression Tourette Syndrome of Improvement (CGI-TS-I) from Week 4 to Week 12
- Change in YGTSS-Global Score (GS) from Baseline to Week 12
- Change in Caregiver Global Impression of Change (CaGI-C) from Week 4 to Week 12
- Change in Gilles de la Tourette Syndrome–Quality of Life Scale for Children and Adolescents (C&A-GTS-QOL) from Baseline to Week12
- Percentage of subjects with a 25% improvement on the YGTSS-TTS
- Percentage of subjects with complete remission of tics on the YGTSS-TTS
- Change in YGTSS-TTS from Baseline to Weeks 4, 6, and 8
- Change in CGI-TS-S from Baseline to Weeks 4, 6, and 8
- Change in CGI-TS-I from Baseline to Weeks 4, 6, and 8
- Change in YGTSS-GS from Baseline to Weeks 4, 6, and 8

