9. TREATMENT OF SUBJECTS

9.1. Description of Study Drug

Table 3:Investigational Product

	Investigational Product				
Product Name	Ecopipam HCl	Placebo			
Dosage Form	Tablets	Matching Tablets			
Unit Dose of Ecopipam HCl	12.5, 50, 75 and 100 mg	Matching unit dose tablets			
Route of Administration	Oral	Oral			
Physical Description	Round, biconvex, light blue film-coated tablet, plain on both side	Round, biconvex, light blue film-coated tablet, plain on both sides			
Manufacturer	Corealis Pharma Inc	Corealis Pharma Inc			

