9.4. Treatment Compliance

During the study period, subject compliance will be monitored by review of the tablet counts at the study site visits. Any violation of compliance will require evaluation by the Investigator and Sponsor or its representative to determine if the subject may continue the study.

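### SAP 10.2 expects one tablet a day where Protocol Table 4 requires one to three, and it divides compliance by an undefined number of study days

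*SAP*

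**What the plan says.** SAP section 10.2 sets the expectation that "Subjects are expected to take 1 tablet of study medication once per day". It defines "compliance (%) = (Sum of Study drug taken= Yes) / (number of days in study) x 100", and adds that the doses actually taken are recorded on the eCRF. "Subjects will be considered compliant overall for study medication if the compliance is" at least 80%. Descriptive statistics for "number of actual tablets taken, number of expected tablets taken, and treatment compliance will be summarized by treatment group".

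Protocol section 9.4 says that "subject compliance will be monitored by review of the tablet counts at the study site visits"; it gives no percentage threshold. Protocol section 9.1 lists unit strengths of "12.5, 50, 75 and 100 mg". Protocol section 10.6, Table 4, shows how many tablets make up each dose by weight band and week.

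On the length of the study, the protocol synopsis lists "Four weeks Screening Phase, Baseline Visit, 4-week Titration Period, 8-week Treatment Period and 2-week Follow-up Period", plus a telephone contact at 30 days. SAP sections 6.2 and 10.1 define duration of exposure as last dose date minus first dose date plus one. Section 10.2 does not use that measure.

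**The concern.** There are two separate faults in one short section.

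First, several prescribed doses cannot be one tablet. SAP section 3.7 itself lists daily doses of 25, 37.5, 150 and 200 mg, and none of these is an available strength. An expected count built on one tablet a day would be too low, by a factor that depends on weight band, and adherent subjects would appear to have taken more drug than prescribed.

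Second, the denominator is not tied to dosing. Subjects remain under observation after the last dose, with visits at 7 and 14 days and a call at 30 days. If any of that time counts as days in study, the percentage falls for reasons unrelated to missed doses, and it falls most for subjects who stop early. The protocol requires subjects who cannot tolerate titration to be discontinued, so early stopping is expected. If it differs between arms, the comparison of compliance by treatment group would partly reflect discontinuation.

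**Working it through.** **Expected tablets.** Inputs are Table 4 tablets per day, with 50, 75 and 100 mg each taken as one tablet because Table 4 shows no multiple for them. The period is 28 titration days plus 56 treatment days = 84 days, taper excluded. The formula is 7 × (Week 1 + Week 2 + Week 3 tablets per day) + 63 × (tablets per day from Week 4 onward). The SAP rule gives 84 × 1 = 84 for everyone.

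| Weight band (kg) | Wk 1 | Wk 2 | Wk 3 | Wk 4 on | Calculation | Tablets | Ratio to 84 | Multi-tablet days |
|---|---|---|---|---|---|---|---|---|
| ≥18 to ≤23 | 1 | 2 | 3 | 3 | 7×6 + 63×3 | 231 | 2.75 | 77 |
| >23 to ≤34 | 1 | 2 | 3 | 1 | 7×6 + 63×1 | 105 | 1.25 | 14 |
| >34 to ≤44 | 1 | 2 | 1 | 1 | 7×4 + 63×1 | 91 | 1.08 | 7 |
| >44 to ≤68 | 2 | 1 | 1 | 1 | 7×4 + 63×1 | 91 | 1.08 | 7 |
| >68 to ≤83 | 2 | 1 | 1 | 2 | 7×4 + 63×2 | 154 | 1.83 | 70 |
| >83 | 2 | 1 | 1 | 2 | 7×4 + 63×2 | 154 | 1.83 | 70 |

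No band reproduces 84.

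**Compliance percentage.** For a subject who doses every day, the score is d / (d + f), where d is dosing days and f is off-drug days counted as in study. The first table column is a completer; the second is a subject who stops at Week 4.

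| Count runs from first dose to | d = 84 | d = 28 |
|---|---|---|
| Last dose (f = 0) | 84/84 = 100% | 28/28 = 100% |
| 7-day visit (f = 7) | 84/91 = 92.3% | 28/35 = 80.0% |
| 14-day visit (f = 14) | 84/98 = 85.7% | 28/42 = 66.7% |
| 30-day call (f = 30) | 84/114 = 73.7% | 28/58 = 48.3% |

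The score is below 80% when d < 4f. A completer fails once f exceeds 84/0.8 − 84 = 21 days. Counted to the 14-day visit, anyone with fewer than 56 dosing days fails (42 days: 42/56 = 75.0%). Counted to the 30-day call the limit is 120 days, so every completer fails. Counting a full 28-day screening period, with no follow-up, gives 84/112 = 75.0%.

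**Taper.** The documents do not state its length. If the 25 mg/day reduction means one step each day (an assumption), it lasts 1 to 7 dosing days by band. Counted in both numerator and denominator, the completer's score is 85.9–86.7% to the 14-day visit and 73.9–75.2% to the 30-day call. Neither range changes which side of 80% the subject falls on.

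**The case against.** The strongest reply is that the percentage is a count of days on which drug was taken, so tablet number never enters it. That stands. A reader might infer that the 80% flag measures tablet strength, or that a child in the lowest band would score 231/84 = 275%. The formula does not produce either result; the one-tablet error is confined to the expected-tablet summary.

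It can also be said that days in study may simply mean the dosing period. The schedule heads the Week 12 column as completion or early termination, and the synopsis places the 30-day call after study completion. On that reading adherent subjects score 100%. Against it, SAP section 10 lets off-drug adverse events run from the day after the last dose to the end of study, and the schedule numbers the follow-up contacts as study visits 9 to 11. So the denominator is undefined and the documents pull both ways. A reader might call it wrong outright; the documents do not support that.

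A reader might also infer that the flag decides membership of the per-protocol set. SAP section 5.4 bases that set on major deviations found at blinded review, and section 5.6 refers their categories to a separate management plan that is not among the documents. Nothing in either document makes a score below 80% a deviation, and the primary analysis uses the mITT set.

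Finally, replacing the formula with tablets taken over tablets prescribed would weight days unequally. In the >23 to ≤34 kg band a missed Week 3 day would count as three tablets and a missed Week 4 day as one. This objection stands, and it is a reason to keep the dose-day numerator.

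**Conclusion.** The one-tablet sentence contradicts Table 4 in all six weight bands. The planned expected-tablet summary would be too low by 8% of the assumed count in the two middle bands and by 175% in the lowest (ratios 1.08 and 2.75). This needs only the assumption that 50, 75 and 100 mg are single tablets; the 25, 37.5, 150 and 200 mg doses exceed one tablet on the listed strengths alone.

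The denominator fault is conditional. A fully adherent completer scores anywhere from 100% to 74% when counted from first dose, depending on which endpoint a programmer chooses, and lower still if screening is included. A fully adherent Week 4 stopper ranges from 100% to 48%. Two analysts could both follow the SAP and classify the same subject differently.

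The consequence visible in the documents is limited to descriptive compliance summaries. The point is worth correcting, and it does not touch the primary analysis.

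**What to change.** In SAP section 10.2:

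- Delete the one-tablet sentence and derive expected tablets from Protocol Table 4 by weight band and study week.
- Keep the yes/no dose-day numerator. Define the denominator as scheduled dosing days from first dose to the last scheduled dose, or to discontinuation of dosing if earlier, and apply the 80% cut to that figure.
- Restrict the numerator to the same days, and report taper compliance separately, so that taper days do not enter one side of the ratio only.

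This needs a few lines of SAP wording and a lookup table of six bands by four dosing periods. Dosing is already recorded on the eCRF, so no new data are collected and no dose or clinical rule changes.

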10.3. Adverse Events / Adverse Drug Reactions

An adverse event (AE) is any untoward medical condition that occurs in a patient while participating in this clinical study. Adverse events will be coded according to the Medical Dictionary for Regulatory Activities (MedDRA 22.0) terminology and the severity of the toxicities will be graded according to the National Cancer Institute (NCI) Common Toxicity Criteria for Adverse Events (CTCAE), v4.03, where applicable. An adverse drug reaction (ADR) means any AE caused by a drug or biologic.

Treatment-Emergent Adverse Events (TEAEs) are those adverse events/adverse drug reactions that are recorded during or following the initiation of study treatment administration, and do not necessarily have a causal relationship to the use of the study medication. Treatment-Emergent Adverse Events (simply referred to as adverse events in summary tables) will be summarized.

The following adverse event summary tables will be summarized by treatment group:

- An overall summary with the number and percentage of patients reporting AEs, serious AEs, grade 3 or higher AEs, treatment-related AEs, serious TEAEs, AEs leading to study treatment discontinuation and AEs with outcome of deaths.
- 2) AEs overall and by system organ class and preferred term.

In this summary, a patient is counted once at the system organ class and once at each preferred term within the system organ class.

- 3) AEs overall and by system organ class, preferred term and initial daily dose level.
- 4) AEs overall and by system organ class, preferred term and region.
- 5) AEs overall and by system organ class, preferred term and weight band.
- 6) AEs overall and by system organ class, preferred term in subjects over 100Kg in weight.
- 7) AEs overall and by system organ class, preferred term and week within the titration phase.
- 8) AEs overall and by system organ class, preferred term and visit within the maintenance phase.
- AEs overall and by system organ class, preferred term and visit within the down titration phase and follow up.
- 10) AEs overall and by system organ class, preferred term and highest CTCAE grade.

In this summary, a patient is counted once at the highest grade for which the event occurred in the system organ class and the highest grade for each unique preferred term within that system organ class. Therefore, patients may only contribute once to each preferred term and once to each system organ class. The missing severity grade will be reported in a separate category.

11) Study-treatment-related AEs overall and by system organ class and preferred term.

All those AEs with relationship to treatment marked as "Possibly Related" or "Probably Related" or missing will be reported in the table.

- 12) Study-treatment related AEs by system organ class, preferred term and Highest CTCAE grade
- 13) AEs leading to study treatment termination by system organ class and preferred term.
- 14) AEs leading to study treatment termination by system organ class, preferred term and highest CTCAE grade
- 15) CTCAE Grade 3 or higher AEs, overall and by system organ class and preferred term
- AEs by maximum severity, maximum relatedness and milestones (titration phase, maintenance phase, taper down, and off study drug).

A Serious Adverse Event (SAE) is an AE which falls into one or more of the following categories:

- a. Results in death
- b. Is life-threatening
- c. Requires inpatient hospitalization or prolongation of existing hospitalization
- d. Results in persistent or significant disability or incapacity
- e. Is a congenital anomaly/birth defect
- f. Is any other important medical event

Serious adverse events will be summarized by treatment group and combined over both treatment groups. A summary by age group (children 6-11 and adolescents 12-17) will also be provided.

17) SAEs overall and by system organ class and preferred term.

In this summary, a patient is counted once at the system organ class and once at each preferred term within the system organ class.

Adverse Events of Special Interest (AESI) for ecopipam include Convulsions, Depression and Suicide/Self Injury, Drug Abuse, Dependence and Withdrawal, Dyslipedaemia, Hepatic Disorders, Hyperglycaemia/New Onset Diabetes Mellitus, NMS, and Psychosis and Psychotic Disorders.

AESI for Parkinsonism include Ataxia, Confusional state, Coordination abnormal, Somnolence, Disturbance in attention, Dyskinesia, Hyperkinesia, Gait disturbance, Memory impairment, Tremor, Vertigo, Agitation, Anxiety, Disturbance in attention, Dystonia, Bradykinesia, Musculoskeletal stiffness, Dysstasia, Gait disturbance, Posture abnormal, Balance disorder, Movement disorder, Movement disorder, Dyskinesia, Muscle rigidity, Coordination abnormal, Muscle contracture, Bradykinesia, Gait disturbance, Terminal insomnia, Nightmare, Poor quality sleep, Sleep disorder, Fatigue, Dizziness, Balance disorder, Restlessness, Amnesia, Confusional state, Dementia, Mental impairment, Speech disorder, Dysphonia, Vocal cord dysfunction, Parosmia, Anosmia, Urinary incontinence, Anxiety, Apathy, Joint stiffness, Reduced facial expression, Confusional state, Flat affect, Constipation, Depression, Dysphagia, Drooling, Fall, Fear of falling, Loss of visual contrast sensitivity, Muscle tightness, Dysgraphia, Dyskinesia, and Weight decreased.

AESI summary tables are listed below:

- 1) AESI for ecopipam overall and by system organ class and preferred term
- 2) AESI for Parkinsonism overall and by system organ class and preferred term.

In this summary, a patient is counted once at the system organ class and once at each preferred term within the system organ class.

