12.4. Recording Adverse Events

Adverse events spontaneously reported by the subject and/or in response to an open question from the study personnel or revealed by observation will be recorded during the study at the investigational site. Clinically significant changes in laboratory values, blood pressure, and pulse can be reported as AEs per the investigator's judgement. However, abnormal values that constitute an SAE or lead to discontinuation of administration of study drug must be reported and recorded as an AE. Information about AEs will be collected from the signing of consent form until the end of the study. SAE information will be collected from signing of consent form until 30 days following the last dose of study drug. The AE term should be reported in standard medical terminology when possible. For each AE, the investigator will evaluate and report the onset (date and time), resolution (date and time), intensity, causality, action taken, serious outcome (if applicable), and whether or not it caused the subject to discontinue the study.

Intensity will be assessed according to the following scale:

- Mild (awareness of sign or symptom, but easily tolerated)
- Moderate (discomfort sufficient to cause interference with normal activities)

• Severe (incapacitating, with inability to perform normal activities)

It is important to distinguish between serious and severe AEs. Severity is a measure of intensity whereas seriousness is defined by the criteria under Section 12.2.1.2. An AE of severe intensity may not be considered serious.

Should a pregnancy of a subject or partner occur, it must be reported and recorded on Sponsor's or Sponsor approved pregnancy form. Pregnancy in itself is not regarded as an AE unless there is a suspicion that an investigational product may have interfered with the effectiveness of a contraceptive medication. Reports of pregnancy must be submitted to Syneos Health Safety & Pharmacovigilance within one business day:

Email Address: [contact] Fax no. Americas: [contact] Fax no. Europe and ROW [name]

The outcome of all pregnancies (spontaneous miscarriage, elective termination, normal birth or congenital abnormality) must be followed up and documented even if the subject was discontinued from the study.

All reports of congenital abnormalities/birth defects are SAEs. Spontaneous miscarriages should also be reported and handled as SAEs. Elective abortions without complications should not be handled as AEs.

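### SAP 10.3 builds five of its 17 numbered adverse event tables on CTCAE grades, while protocol 12.4 asks only for mild, moderate or severe, and nothing maps one scale to the other

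*SAP*

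**What the plan says.** Protocol 12.4 lists what is recorded for each adverse event: "the investigator will evaluate and report the onset (date and time), resolution (date and time), intensity, causality, action taken", followed by outcome and discontinuation items. "Intensity will be assessed according to the following scale", and three levels follow: "Mild (awareness of sign or symptom, but easily tolerated"), "Moderate (discomfort sufficient to cause interference with normal activities") and, at the top, "Severe (incapacitating, with inability to perform normal activities"). No CTCAE grade is requested. Protocol 13.2.2 plans summaries of treatment-emergent events by severity and names no grading system. In the protocol text available, CTC and NCI appear only in the abbreviation list (section 4).

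SAP 10.3 takes another route: "the severity of the toxicities will be graded according to the National Cancer Institute (NCI) Common Toxicity Criteria for Adverse Events (CTCAE), v4.03". The sentence goes on to limit this to cases where it is applicable, without saying which those are. The numbered tables that follow include a grade 3 or higher entry in the overall summary (table 1), three breakdowns by highest grade (tables 10, 12 and 14), and table 15: "CTCAE Grade 3 or higher AEs, overall and by system organ class and preferred term". A note under table 10 adds: "The missing severity grade will be reported in a separate category". SAP section 12 declares no departure from the protocol's planned analysis.

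**The concern.** An analysis plan should be able to produce its tables from the data the protocol tells sites to collect. Here the protocol describes one severity scale and the SAP tabulates another. Neither document gives a crosswalk, names who assigns a grade, or says when grading takes place.

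Safety is a secondary objective (protocol 6.2) in a paediatric population, and the affected tables cover severity overall, among treatment-related events, among events leading to termination, and in the one table restricted to the higher grades. If grades are not in the database, the programmer must either deliver empty or ungraded tables or obtain grades by some rule settled later. A rule settled late leaves discretion over how events are classified, possibly once treatment assignments are known, although investigators will already have rated every event on a usable scale.

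**Working it through.** The plan states no figure to reproduce. The check is a comparison of the two documents and a count.

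**Step 1: the scales.** The protocol scale has three levels and ends at severe. The SAP scale has a threshold at grade 3 and, by the words "or higher" in its own table title, at least one level above it. The two therefore do not match level for level, and no passage says how one converts to the other.

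**Step 2: which numbered tables in SAP 10.3 need a grade.** I assume that the note on missing grades under table 10 also applies to tables 12 and 14, which the SAP does not state.

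| Table | Where the grade enters | Content if no grade is recorded or assigned |
|---|---|---|
| 1 | one row, grade 3 or higher | that row empty; other rows unaffected |
| 10 | highest grade, all events | all events under missing grade |
| 12 | highest grade, related events | all events under missing grade |
| 14 | highest grade, events leading to termination | all events under missing grade |
| 15 | grade 3 or higher only | empty |

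Four whole tables plus one row: 4 + 1 = 5 of 17 numbered tables (5/17 = 29%). The remaining 17 − 5 = 12, and the two separate tables for events of special interest, need no grade.

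**Step 3: what the ungraded case means.** With no grade, mild, moderate and severe events are all ungraded alike. Table 10 would then add nothing to table 2, table 12 nothing to table 11, and table 14 nothing to table 13, because each falls back to counts by system organ class and preferred term.

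**Step 4: what happens if someone maps the scales.** Suppose severe were taken as grade 3. This is an assumption; neither document states it. Table 15 and the table 1 row would then fill, but grades above 3 could not be told apart on intensity alone. Deaths and life-threatening events are identified only through the criteria for serious events.

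**Step 5: what severity reporting remains.** The opening text of SAP section 10 plans summaries by severity for treatment-emergent events, and again for events in the treatment, taper and off-drug periods. Table 16 gives maximum severity by study milestone. None of these names CTCAE, and all can be produced from the three-level rating.

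**The case against.** The strongest reply has four parts.

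First, the grading sentence is qualified, so it need not bind every event. That is fair as a reading of the sentence, but the SAP never says when CTCAE applies or what replaces it otherwise, and the tables that depend on the grade carry no such qualifier.

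Second, the eCRF, its completion guidelines and the table shells are not in the documents, and a grade may be captured there. This stands. A reader might infer that the tables have no data; the documents show only that the protocol text does not ask for a grade. If the eCRF does collect one, two scales coexist with no rule relating them, so a reconciliation is still needed.

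Third, CTCAE grading is itself written into the SAP, so it cannot be called unplanned. This also stands. What is missing is who grades, when, and how the grade relates to the recorded intensity.

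Fourth, severe events by arm remain visible in the section 10 summaries and table 16, and the gravest outcomes through serious events (table 17), deaths (table 1) and terminations (table 13). This is correct and limits the harm. One reservation: the only severity scale that the SAP names for adverse events is CTCAE, so it should say that severity in those summaries means the investigator's intensity rating.

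**Conclusion.** The mismatch is real: a stated SAP rule does not fit the data that the protocol describes, the gap touches 5 of 17 numbered AE tables, and section 12 does not acknowledge it. The consequence is conditional. If the eCRF captures no grade and nobody assigns one, table 15 and the grade 3 or higher row of table 1 are empty and tables 10, 12 and 14 show everything as ungraded. If grades are assigned, this happens by a rule that neither document gives.

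Three stronger inferences are not supported. A reader might conclude that severe events in particular would be routed to the missing category; nothing in SAP 10.3 does that, and without grades all intensities would be treated the same. A reader might conclude that the adverse event reporting as a whole rests on CTCAE; 12 of the 17 numbered tables do not use it. And a reader might conclude that the comparison of severe events between arms is lost; the section 10 summaries and table 16 can still supply it.

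The primary endpoint and the hierarchy of tested endpoints are untouched. The point should be corrected before unblinding, and it does not threaten the trial's efficacy conclusion.

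**What to change.** Preferred, before unblinding: in SAP 10.3, base tables 10, 12 and 14 on maximum protocol intensity (mild, moderate, severe); replace grade 3 or higher with severe adverse events in table 15 and in the overall summary; and delete the CTCAE grading sentence for adverse events. State that severity in section 10 and table 16 means the same intensity rating. This costs SAP wording and table shells and needs no new data.

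If CTCAE is to be kept: prespecify before unblinding how grades are assigned and by whom, and how they relate to the recorded intensity; say when the qualifier applies; and record the departure from the protocol in SAP section 12. If the eCRF holds no grade, this option also costs the work of grading the events under the blind.
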